#### **9.5.6.3.4 Week 48/End-of-Treatment 2**

Week 48 is the final visit of the open-label Treatment Period. Trial drug is not administered.

- Obtain blood samples for hematology and fasting chemistry (including thyroid and HbA1c) analysis.
- Collect urine sample for a pregnancy test for females of childbearing potential.
- Perform visual acuity assessment.
- Measure weight.
- Perform efficacy assessments (proptosis, **CCI** [REDACTED] and GO-QoL questionnaire). The **CCI** will not need to be performed on the same day as other Week 48 assessments as long as it is performed within the visit window.
- Perform CAS.
- Record vital signs.
- Collect blood samples for immunogenicity testing. Collect a single blood sample for PK analyses.
- Inquire about AEs and concomitant medication use.
- Take photograph of the patient's eyes for those patients who have consented.
- Enter visit data in the EDC system.

Patients will be discharged from the site after all procedures have been completed and enter the Follow-up Period.

#### **9.5.6.4 Follow-up Period (End-of-Study/Trial)**

All patients will be contacted via phone or email 30 days after the Week 24 (responders and non-responders who choose not to receive open-label TEPEZZA) or Week 48 (non-responders who receive open-label TEPEZZA) Visit. Inquire about AEs and concomitant medication use.

The end of the trial is defined as the date of the last patient contact at the end of the Follow-up Period.

## 9.6 Statistical Methods and Determination of Sample Size

### 9.6.1 Endpoints

#### 9.6.1.1 Primary Endpoint

The primary efficacy endpoint is the change from Baseline at Week 24 in proptosis in the study eye.

#### 9.6.1.2 Other Efficacy Endpoints

1. The proptosis responder rate (percentage of patients with a  $\geq 2$ -mm reduction from Baseline in proptosis in the study eye, without deterioration [ $\geq 2$ -mm increase] of proptosis in the fellow eye) at Week 24.
2. The change from Baseline at Week 24 in the GO-QoL questionnaire appearance and visual functioning subscales.

3.

4.

5.

The image consists of the letters 'CCI' in a large, bold, red sans-serif font. They are centered on a solid black rectangular background.

#### 9.6.1.3 Pharmacokinetic and Anti-drug Antibody Endpoints

1. The peak and trough concentrations of TEPFZZA.
2. The ADA incidence and titers.

#### 9.6.1.4 Safety and Tolerability Endpoints

1. The incidence of TEAEs, SAFs, TEAEs resulting in premature discontinuation of treatment and AFSIs (infusion reactions, hyperglycemia, hearing impairment, new onset inflammatory bowel disease and exacerbation of inflammatory bowel disease).
2. The incidence of  $\geq$ Grade 3 TEAEs.
3. The change from Baseline to each scheduled visit in vital signs (blood pressure, heart rate, respiratory rate and temperature).
4. The results of best-corrected visual acuity.
5. The incidence of  $\geq$ Grade 3 fasting glucose values.
6. The change from Baseline to each scheduled visit in laboratory evaluations (hematology and fasting chemistry [including thyroid panel and HbA1c]).

#### 9.6.1.5 Exploratory Endpoint

#### 9.6.2 Analysis Sets

Efficacy analyses will be performed on the intent-to-treat (ITT) analysis set, consisting of patients who are randomized to trial drug (either TEPEZZA or placebo). Safety analyses will be performed on the safety set, consisting of patients who receive at least 1 dose of trial drug. The PK analysis set will include all patients who receive at least 1 dose of trial drug and have at least 1 post-dose PK sample.

#### 9.6.3 Primary Efficacy Endpoint Analysis

The primary efficacy analysis will be conducted on the ITT analysis set. A Mixed-Model for Repeated-Measures (MMRM) analysis of covariance model fitting to the individual change from Baseline scores for the study eye will be used for the analysis of change from Baseline in proptosis. The model includes Baseline score, treatment group, visit, visit-by-treatment and visit-by-Baseline score as covariates. The unstructured covariance will be used. The treatment difference (TEPEZZA minus placebo) based on the estimated least squares (LS) means at Week 24 will be presented with associated standard error (SE), 95% confidence interval (CI) and p-value.

#### 9.6.4 Other Efficacy Endpoints Analyses

The other endpoints of the proptosis responder rate, CCI [REDACTED]

CCI

CCI. A 95% exact CI will be provided for each risk difference observed between the treatment groups. Patients whose Week 24 evaluation is missing will be considered treatment failures (non-responders) for the responder analysis.

CCI [REDACTED]

A large, bold, red text 'CCI' is centered on a solid black rectangular background.

CCI [REDACTED]

Remaining other or exploratory endpoints analyzing change from Baseline (such as in GO-QoL, CCI [REDACTED] will use the same MMRM method specified for the primary efficacy endpoint.

Descriptive summaries for observed and change from Baseline values in CCI [REDACTED]

#### 9.6.5 Safety and Tolerability Analyses

The number and percentage of patients experiencing at least 1 occurrence of a TEAE, SAE, TEAE resulting in premature discontinuation of treatment and AFSI for each unique System Organ Class and Preferred Term will be summarized by treatment group. TEAEs and SAEs will also be summarized by severity and relationship to trial drug, as assessed by the Investigator. Grade 3 and higher TEAEs, as graded by the National Cancer Institute Common Terminology Criteria for Adverse Events (NCI-CTCAE), will also be summarized for each unique System Organ Class and Preferred Term.

The number and percentage of patients in each treatment group using concomitant medications will be summarized by Anatomical Therapeutic Chemical Level 4 term and Preferred Term.

For best-corrected visual acuity, shift tables will be presented providing the count of patients in each treatment group with each type of finding (normal, abnormal – not clinically significant, or abnormal – clinically significant) at Baseline compared to each postbaseline visit.

Descriptive summaries of observed and change from Baseline values will be presented for each vital sign parameter by treatment group and visit. A shift table for vital signs by NCI-CTCAE grade and visit will be generated by treatment group.

Safety laboratory (hematology and fasting chemistry [including thyroid panel and HbA1c]) values and change from Baseline will be summarized by visit and treatment group using descriptive statistics. The laboratory assessment will be categorized as low, normal or high based on normal ranges and graded using the NCI-CTCAE grading scale, when available. Shift tables using categories of low, normal and high from Baseline to each visit will be generated by treatment group. Additionally, a shift table for glucose by NCI-CTCAE grade and visit will be generated by treatment group. Summaries will be provided separately for hyperglycemia.

The rate and titer of positive ADA samples will be summarized by visit and treatment group using descriptive statistics. Teprotumumab peak and trough (i.e., prior to dose) concentrations will also be summarized by visit using descriptive statistics.

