#### **Risk of Hypersensitivity (Infusion-related events)**

- Administration of mAbs may cause infusion-related symptoms, such as fever, chills, hypotension, shortness of breath, skin rash and headache. Such reactions typically occur

during or shortly after the infusion of mAbs and are usually associated with the first infusion. Their incidence and severity typically decrease with subsequent infusions. Severe infusion-related reactions might be clinically indistinguishable from anaphylactic reactions.

- Infusion-related events observed with teprotumumab to date have not been anaphylactic in nature. However, because of the protein nature of teprotumumab and the potential for infusion-related reactions and hypersensitivity reactions, teprotumumab should be administered in a setting with emergency equipment and staff who are trained to monitor medical situations and respond to emergencies. For the first 3 infusions, patients should be monitored for any events during infusion and for 60 minutes after completion of infusion. For subsequent infusions (the fourth dose and beyond), patients who have not previously experienced an infusion reaction should be monitored during the infusion and for at least 30 minutes after the infusion.
- Patients who exhibit immediate hypersensitivity reactions or infusion-related reactions during an infusion of teprotumumab should have the infusion interrupted or the infusion rate slowed. Symptomatic treatment, e.g., antipyretics, antihistamines and/or corticosteroids, oxygen, beta agonists and IV fluids, should be administered to the patient. Following an immediate hypersensitivity reaction or infusion-associated reaction, vital signs (temperature, blood pressure, pulse and respiratory rate) will be monitored every 5 minutes until stable, and then every 15 minutes for 2 additional determinations. The infusion may be restarted upon complete resolution of symptoms except in the case of patients who experience an anaphylactic reaction of life-threatening intensity; these patients should be removed from the trial.

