10.3 Vital Sign and Weight Measurements

Vital signs measurements will include systolic and diastolic blood pressures, heart rate, respiratory rate, height, weight, BMI and temperature.

Descriptive summaries of observed and change from Baseline values will be presented for each vital sign parameter by treatment group and visit for each treatment period.

A summary table for weight loss and a shift table for hypertension by NCI-CTCAE grade will be generated by treatment group and visit for each treatment period.

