A patient listing of serum concentration-time data will be presented by visit. Teprotumumab peak and trough (i.e., prior to dose) concentrations will be summarized by visit and ADA status (overall positive vs cumulative negative; only to be performed if more than 2 patients receiving TEPEZZA treatment with a positive ADA observed in the trial) using descriptive statistics. The analyses will be based on the PK analysis set in each treatment period.

Further, the mean and CV% (calculated as 100%*SD/mean) of pre-dose serum concentrations will be provided by visit in the subset of patients who are confirmed ADA positive, NAb positive (if applicable) and ADA negative for each visit. This analysis will be provided for the PK Population.

13. Changes in the Planned Analysis

- To ensure the control of the overall Type I error rate in analyzing multiple efficacy endpoints, the process to test individual efficacy endpoints has been added in the SAP section 5 and section 9, as an addition to the protocol.
- TEPEZZA Baseline is defined in the SAP for analysis relative to baseline in the open-label treatment period.
- TEPEZZA study day is defined in the SAP for analysis relative to first dose date during the open-label treatment period.

- To better characterize GO-QoL, analyses of patients with minimal clinically important change in the GO-QoL subscales will be provided.
- Summary and shift tables for chemistry (excluding glucose) will be based on all records (fasting and non-fasting records).

14. References

Heitjan DF and Little RJA. Multiple Imputation for the Fatal Accident Reporting System. *Journal of the Royal Statistical Society, Series C*. 1991; 40:13–29.

Rubin DB. *Multiple Imputation for Nonresponse in Surveys*. New York: John Wiley & Sons. 1987.

Schenker N and Taylor JMG. Partially parametric techniques for multiple imputation. *Computational Statistics & Data Analysis*. 1996; 22:425-446.

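### SAP 10.3 narrows the protocol's CTCAE-grade shift table for vital signs to hypertension, and SAP section 13 does not declare the change

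*Protocol*

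**What the plan says.** Protocol 9.6.5, with the same sentence in the synopsis, states: "A shift table for vital signs by NCI-CTCAE grade and visit will be generated by treatment group". It names no single parameter and no direction of change. Protocol 9.6.1.4 shows what the protocol counts as vital signs: "The change from Baseline to each scheduled visit in vital signs (blood pressure, heart rate, respiratory rate and temperature".

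SAP 10.3 gives two kinds of output. The first applies to every parameter: "Descriptive summaries of observed and change from Baseline values will be presented for each vital sign parameter by treatment group and visit for each treatment". The second is graded and narrower: "a shift table for hypertension by NCI-CTCAE grade will be generated by treatment group and visit for each treatment period", accompanied by a summary table for weight loss.

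SAP section 13, "Changes in the Planned Analysis", is where departures from the protocol are recorded. It has five entries: the testing order for efficacy endpoints, TEPEZZA Baseline, TEPEZZA study day, the added GO-QoL responder analysis, and the fasting status of chemistry records. None concerns vital signs.

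Infusion reactions are an adverse event of special interest (AESI) in Protocol 9.5.3.1.1.5. The risk text there lists "infusion-related symptoms, such as fever, chills, hypotension, shortness of breath, skin rash and headache" for monoclonal antibodies in general. Protocol 9.4.6.3.2 gives tachycardia and a transient rise in blood pressure among its examples of immediate infusion-associated events.

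**The concern.** A shift table answers a question that a table of means does not: how many patients in each arm moved from an acceptable value at Baseline to an abnormal one, and by how many grades. The protocol promised that count for vital signs. The SAP keeps it for one parameter in one direction, high blood pressure, and does not say that it has dropped the rest or why.

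The dropped items include three that the protocol associates with infusion reactions: raised temperature, low blood pressure and fast heart rate. An undeclared cut to a safety output that touches a named AESI is hard to explain once the data are unmasked, even if the reason was purely technical.

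**Working it through.** The plan states no figure on this point, so the check compares the texts, with one illustrative calculation.

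**Step 1. Set the commitments side by side.**

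| Vital sign | Graded shift table, Protocol 9.6.5 | Graded shift table, SAP 10.3 | Descriptive summary, SAP 10.3 |
|---|---|---|---|
| Blood pressure, high | covered | yes | yes |
| Blood pressure, low | covered (no direction excluded) | no | yes |
| Heart rate | covered | no | yes |
| Respiratory rate | covered | no | yes |
| Temperature | covered | no | yes |

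Weight is not in the protocol's list of vital signs. The weight-loss summary is therefore an addition and does not replace any of these rows.

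**Step 2. Rule out a version gap.** The SAP (section 1) is based on administrative change 1 to protocol V4.0. The V5.0 summary table of changes shows edits to Sections 7.1.1, 7.1.2, 9.5.3.1.1.5 and 16, and none to 9.6.5. The vital-sign commitment was thus not introduced after the SAP's base version, as far as the change table shows. Redaction does not explain the difference either, because both sentences are fully legible.

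**Step 3. Ask whether it was declared.** The last of the five entries in SAP section 13 reads "Summary and shift tables for chemistry (excluding glucose) will be based on all records (fasting and non-fasting records". A change at that level of detail was thought worth recording; the vital-sign restriction was not.

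**Step 4. See what the remaining outputs provide.**
- SAP sections 5 and 10 define the continuous summaries as mean, SD, median, quartiles, minimum and maximum. Extremes are therefore visible for both observed and change values.
- SAP section 5 also lists the raw data behind the tables.
- SAP 10.1.1 and 10.1.3 count treatment-emergent adverse events (TEAEs) by arm, term and severity. SAP 10.1.6 does the same for AESIs by term. These are counts of reported events, not of measured values.
- SAP 10.1 places the signs and symptoms of infusion reactions in a by-subject listing.

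**Step 5. Illustrate what is lost.** Take 38 TEPEZZA patients (Protocol 9.6.7) and assume, for illustration only, that two of them each have a 40 mmHg systolic fall.
- Share of the arm: 2 / 38 = 5.3%.
- Movement of the mean change: 2 × 40 / 38 = 2.1 mmHg.
- With one such patient: 1 / 38 = 2.6% and 40 / 38 = 1.1 mmHg.
- One patient with a 2 °C rise moves mean temperature change by 2 / 38 = 0.05 °C.

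The mean barely registers these patients. The minimum (or, for temperature, the maximum) does register them, but it can be the same whether one patient or several crossed a limit, and it does not give their category at Baseline. The missing item is the count.

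**Step 6. Ask how much a by-visit table could catch.** Protocol 9.5.3.4 schedules post-infusion readings on Day 1 and Week 3 for everyone, and at Weeks 24 and 27 for open-label patients. On other infusion days the scheduled reading is taken before the infusion. Those four visits are the first two infusions of each period, and Protocol 9.5.3.1.1.5 says that such reactions usually go with the first infusion. The table would therefore cover part of the relevant time, not all of it.

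**The case against.** The strongest case against is that nothing important is lost. The vital-sign endpoint is change from Baseline to each visit, and SAP 10.3 delivers it in full. Safety output is descriptive, with no hypothesis tests. The definition in Protocol 9.5.3.1.1.1 makes any unfavorable sign reportable, so a clinically important fever, fall in blood pressure or tachycardia should reach the TEAE tables. The SAP's hypertension table covers the blood-pressure rise that Protocol 9.4.6.3.2 names. The fever and hypotension wording came in with V5.0, after the version on which the SAP rests. CTCAE may not grade every vital sign from a measurement.

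Most of this stands, and it limits the size of the point. A reader might infer that these signs now get no categorical table at all, or vanish into arm means unless an investigator reports an event. The documents do not support that: reported events are counted by arm, extremes appear in the summary tables, and raw values are listed.

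Two parts do not answer the point. First, the late arrival of the fever and hypotension wording does not matter to the commitment itself, which covers vital signs generally and is not among the V5.0 edits. Second, gradeability is a possible reason, but the documents do not reproduce the CTCAE criteria, so it cannot be judged from them, and the SAP does not offer it.

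**Conclusion.** The discrepancy is real and undeclared. The protocol promises a graded shift table for vital signs; the SAP provides one for hypertension. What is lost is the count, by arm and visit, of patients whose measured temperature, heart rate, respiratory rate or low blood pressure changes category.

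The consequence is modest. No endpoint is lost, no inference is affected, and reported events are still tabulated. The figures of 2.1 mmHg and 0.05 °C rest on assumed patients and show only that the mean is insensitive in an arm of 38; they are not estimates of missed harm. It would also be too strong to say that the SAP removed tables that could certainly have been produced, since that depends on which vital signs CTCAE can grade from measured values.

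The point rests on reading vital signs in Protocol 9.6.5 as the four parameters listed in Protocol 9.6.1.4, which is the natural reading.

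**What to change.** In SAP 10.3, restore the protocol's by-visit shift table, by arm and treatment period, for every vital sign that CTCAE can grade from measured values, with low as well as high blood pressure. Include the post-infusion readings at the visits where they are collected. For any vital sign that cannot be graded in this way, say so and give the reason in SAP section 13.

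A column for the worst on-treatment value, and prespecified low/normal/high limits for parameters without a grade, would be useful but are optional. Neither is part of the table the protocol promised.

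The cost is a few more descriptive tables and a short edit to the SAP. No new data, no change in trial conduct and no change to the primary analysis are needed.

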#### **9.6.6 Interim Analyses**

No interim analyses are planned.

#### **9.6.7 Sample Size and Power Considerations**

A total of 57 patients (38 in the TEPEZZA group and 19 in the placebo group) will be enrolled in the trial to detect at least a 2-mm mean difference between the 2 treatment groups in the change from Baseline of proptosis values at Week 24 in order to have 81% power at the 2-sided 0.05 level of significance. The sample size was determined assuming that the mean difference in proptosis change between the 2 groups is at least 2.0 mm (clinically relevant) and the standard deviation of proptosis change values is 2.5 for both groups (larger than observed in Phase 2 and Phase 3 active TED trials).

#### **9.7 Changes in the Conduct of the Trial**

If any modifications in the trial design, dosages, parameters, patient selection or any other sections of the protocol are indicated or required, the Investigator will consult with the Sponsor before any such changes are instituted. Modifications will be accomplished through formal amendments to this protocol by the Sponsor that will be approved by the appropriate IRB.

The Sponsor's Medical Monitor will consider any requests for exceptions to protocol entry criteria on a case-by-case basis. The Investigator or other health professional in attendance must contact the Sponsor as soon as possible. All protocol deviations and the reasons for such deviations **must** be documented in the eCRF. In the event of a protocol deviation, the Investigator and Sponsor's Medical Monitor will determine whether the patient should continue participation in the trial.

The Sponsor has a legal responsibility to report fully to regulatory authorities all results of administration of investigational drugs to humans. No investigational procedures other than those described in this protocol will be undertaken on the enrolled patients without the agreement of the IRB and Sponsor.

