### 9.3.2 Exclusion Criteria

Patients will be ineligible for trial participation if they meet **any** of the following criteria:

1. Decreased best-corrected visual acuity due to optic neuropathy, defined by a decrease in vision of 2 lines on the Snellen chart, new visual field defect or color defect secondary to optic nerve involvement within the last 6 months.
2. Corneal decompensation unresponsive to medical management in the study eye.
3. Decrease in proptosis of  $\geq 2$  mm in the study eye between Screening and Baseline.
4. Prior orbital irradiation or orbital decompression in the study eye.
5. Prior strabismus surgery.
6. Alanine aminotransferase or aspartate aminotransferase  $>3 \times$  the upper limit of normal or estimated glomerular filtration rate  $\leq 30$  mL/min/1.73 m^2 at Screening.
7. Use of any steroid (IV, oral, steroid eye drops) for the treatment of TED or other conditions within 3 weeks prior to Screening. Steroids cannot be initiated during the trial. Exceptions include topical and inhaled steroids and steroids used to treat infusion reactions.
8. Any treatment with rituximab (Rituxan® or MabThera®) within 12 months prior to the first infusion of trial drug or tocilizumab (Actemra® or Roactemra®) within 6 months prior to the first infusion of trial drug. Use of any other non-steroid immunosuppressive agent within 3 months prior to the first infusion of trial drug.
9. Any previous treatment with TEPEZZA, including previous enrollment in this trial or participation in a prior teprotumumab trial.
10. Treatment with any mAb within 3 months prior to Screening.
11. Identified pre-existing ophthalmic disease that, in the judgment of the Investigator, would preclude trial participation or complicate interpretation of trial results.

12. Use of an investigational agent for any condition within 60 days or 5 half-lives, whichever is longer, prior to Screening or anticipated use during the course of the trial.
13. Malignant condition in the past 12 months (except successfully treated basal/squamous cell carcinoma of the skin or cervical cancer *in situ*).
14. Pregnant or lactating women.
15. Current drug or alcohol abuse or history of either within the previous 2 years, in the opinion of the Investigator or as reported by the patient.
16. Known hypersensitivity to any of the components of TEPEZZA or prior hypersensitivity reactions to mAbs.

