#### **9.3.4.3 Screen Failures**

Patients who do not meet all the inclusion criteria or meet any of the exclusion criteria will be considered screen failures. Screen failures may be allowed to rescreen for the trial if both the Investigator and Sponsor are in agreement regarding rescreening.

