5.3 Analysis Set

5.3.1 Intent-to-Treat (ITT)

The ITT analysis set is comprised of all patients who are randomized to receive study drug (either TEPEZZA or placebo). This will be the primary analysis set for efficacy analysis for each treatment period. Patients will be analyzed according to their randomized treatment assignment.

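### Protocol 9.7 opens an unlimited case-by-case route to exceptions from any entry criterion, in conflict with the screen-failure rule in 9.3.4.3

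*Protocol*

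**What the plan says.** Four places in the Protocol bear on who may enter.

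- Section 9.7, second paragraph: the Sponsor's Medical Monitor "will consider any requests for exceptions to protocol entry criteria on a case-by-case basis".
- Section 9.7, first paragraph: the amendment rule opens "If any modifications in the trial design, dosages, parameters, patient selection or any other sections of the protocol are indicated or required" and goes on to give the mechanism: "Modifications will be accomplished through formal amendments to this protocol by the Sponsor that will be approved by the appropriate IRB".
- Section 9.3.4.3: "Patients who do not meet all the inclusion criteria or meet any of the exclusion criteria will be considered screen failures". The only way back is rescreening, which needs the agreement of both Investigator and Sponsor.
- Section 9.3.2: the exclusion list opens "Patients will be ineligible for trial participation if they meet" any item on it. No item carries an exception by sponsor decision.

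For the analysis, SAP 5.3.1 states: "The ITT analysis set is comprised of all patients who are randomized to receive study drug". Protocol 9.6.3 adds: "The primary efficacy analysis will be conducted on the ITT analysis set". The SAP expects that some ineligible patients may be enrolled. Section 6.2 has an eligibility category among major deviations, and section 7.3 summarizes unmet criteria by treatment group.

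**The concern.** A site that holds an exception from the Medical Monitor cannot follow both 9.7 and 9.3.4.3. One section says the patient may be considered for entry; the other says the patient is a screen failure. A protocol should not leave a site to choose between them.

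The clause also has no boundary. It covers every entry criterion alike. Inclusion criteria 3 to 5 in 9.3.1 define stable, chronic disease by time since diagnosis, CAS and amount of proptosis, so they fix the population to which the result applies. Other criteria protect patients: the HbA1c limit for diabetics, remission of inflammatory bowel disease, pregnancy, and earlier hypersensitivity to monoclonal antibodies. Nothing in 9.7 separates criteria that might be relaxed from those that must not be.

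Once such a patient is randomized, the analysis cannot undo the decision. The patient is in the ITT set and contributes to the primary result in a trial of only 57 patients.

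**Working it through.** The point is mainly one of text, so the passages are set against each other first. The arithmetic follows.

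**1. Section 9.7 (exceptions) against 9.3.4.3 and 9.3.2.** The screen-failure rule applies to a patient who misses any inclusion criterion or meets any exclusion criterion. Neither section refers to 9.7 or allows for an exception. The conflict is direct.

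**2. Section 9.7 (exceptions) against 9.7 (amendments).** The amendment rule names patient selection and requires IRB approval. The exception sentence has no IRB step. The conflict is softer, because the first paragraph concerns changes to the protocol, while a single-patient exception can be read as a deviation from an unchanged protocol.

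**3. What happens to the patient in the analysis.** ITT membership depends on randomization alone, so a patient entered under an exception is in the primary analysis. That is correct ITT practice; the fault lies in the entry decision. The only planned analysis that could leave the patient out is the supplementary per-protocol analysis (SAP 5.3.3 and 9.2.3). It removes major violations that call the validity of the data into question, as judged at masked review. The SAP does not say whether a sponsor-granted exception is such a violation.

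**4. Direction of any effect.** Under 9.4.7, randomization follows completion of the Baseline procedures. Exceptions are therefore decided before allocation and should fall on the two arms in proportion. Dilution is possible; systematic bias between arms is not expected.

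**5. The plan's own figure.** Inputs from Protocol 9.6.7: 38 and 19 patients, difference 2.0 mm, SD 2.5 mm, two-sided alpha 0.05, stated power 81%.

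- SE of the difference = 2.5 × √(1/38 + 1/19) = 0.70 mm
- Power ≈ Φ(2.0/0.7024 − 1.96) = Φ(0.887) = 81.25%
- The noncentral t version with 55 degrees of freedom gives 79.9%

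The stated power reproduces, so no numerical error is involved.

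**6. Why no size is given.** Suppose a share f of both arms entered under exceptions and had no treatment effect, with the SD unchanged. The difference becomes 2.0 × (1 − f), and power by the normal formula is:

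- f = 5%: difference 1.9 mm, power 77.2%
- f = 10%: difference 1.8 mm, power 72.7%
- f = 20%: difference 1.6 mm, power 62.5%

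If these patients kept half the effect, the difference would be 2.0 × (1 − f/2). A share of 10% would then give 1.9 mm and 77.2%, and a share of 20% would give 1.8 mm and 72.7%. If they responded like eligible patients and varied no more, power would not change. Both f and the response are assumptions, and the documents support no value for either. These figures show how widely the answer depends on the assumptions; they do not estimate a loss.

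**The case against.** The strongest case against the point runs as follows. The Medical Monitor only undertakes to consider requests, and nothing says that one will be granted. The sentence can be read as a specific provision that qualifies the general screen-failure rule. Deviations and their reasons must be recorded in the eCRF, after which "the Investigator and Sponsor's Medical Monitor will determine whether the patient should continue participation in the trial". The SAP tabulates eligibility deviations by arm and repeats the primary analysis on the per-protocol set.

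Part of this stands. Exceptions are possible rather than certain, and the conflict with the amendment rule is arguable. But if 9.7 was meant to qualify 9.3.4.3, neither section says so. The recording and tabulation come after entry, so they document the problem without preventing it.

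Three stronger readings may tempt a reader, and the documents do not support them.

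- **A shift in millimetres.** Protocol 7.2 gives −1.2 mm and −0.48 mm, and a reader might take the gap as active against inactive disease. The first figure is the study-eye mean at Week 72 of all followed placebo patients (n=35), not of active patients. The second belongs to 31 patients selected by a fellow-eye CAS of 3 or less, whereas this trial requires 1 or less; the eye measured is not stated. If the 31 are among the 35 and both figures are study-eye values, the other 4 would average (35 × −1.2 + 31 × 0.48)/4 = −6.8 mm, which is implausible. With a non-study-eye mean of −0.43 mm, the midpoint of its printed interval (−1.07 to 0.21), the same sum gives (35 × −0.43 + 31 × 0.48)/4 = −0.04 mm. The subtraction therefore probably mixes eyes.
- **A certain loss of power.** This needs a number of exceptions and a weaker response. For patients with active disease a weaker response cannot be presumed, since Protocol 7.1.2 and 7.2 report proptosis improvement in the earlier trials in active TED.
- **Automatic loss from the per-protocol set.** The SAP leaves that to masked review.

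**Conclusion.** The concern holds as an inconsistency in the eligibility rules. The exception sentence in 9.7 conflicts directly with 9.3.4.3 and 9.3.2 and sits poorly with the amendment rule in its own section. The likely consequences are a less well-defined population, possible dilution, and exposure of patients whom the safety criteria were meant to exclude. The finding of no expected bias between arms rests on exceptions being settled before randomization. The ITT definition is sound and the stated power is reproduced. The size of any effect on the result is unknown. This is a minor point, worth making because it is almost free to correct.

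**What to change.** 1. In Protocol 9.7, delete the sentence on exceptions and state that none are granted to entry criteria.
2. State that changes to eligibility are made by IRB-approved amendment, and that a patient who does not meet the criteria is a screen failure who may be rescreened under 9.3.4.3.
3. In the SAP, say that any ineligible patient who is nevertheless randomized stays in the ITT set, and that the masked review before the Week 24 lock decides whether that patient is left out of the per-protocol set.

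The cost is one deleted sentence and a few lines of text, with possibly slightly slower enrolment. The sample size, primary model and primary analysis set are unchanged.
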